ClinicalTrials.gov Document Upload

DOCUMENT DATE (IRB APPROVAL):

03-Jan-2024

NCT NUMBER:

NCT05938816

OFFICIAL STUDY TITLE:

Feasibility and acceptability of stress induction, physiological data collection, and Mindfulness-Based Stress Reduction among combat veterans with PTSD

INVESTIGATOR NAME:

[name], MCR

ORGANIZATION:

Oregon Health & Science University

1) Protocol Title

Feasibility and acceptability of stress induction, physiological data collection, and Mindfulness-Based Stress Reduction among combat veterans with PTSD

2) Objectives

Objectives are to gather feasibility and acceptability of key study elements (e.g., stress induction via cognitive stressor, physiological data collection including respiration, blood pressure, and heart rate, and the target intervention Mindfulness-Based Stress Reduction) among combat veterans experiencing PTSD symptoms to support a future K23 grant resubmission. Specific Aims are as follows:

Aim 1: Assess feasibility and participant acceptability of intervention and randomization procedures.

Aim 1A: Examine acceptability of MBSR via qualitative data gathered during a post-intervention focus group.

Aim 1B: Assess feasibility of recruiting and acceptability of randomizing participants to an MBSR or active control condition. Recruitment, differential retention, and home practice completion rates will be examined.

Aim 2: Assess feasibility and participant acceptability of concurrent stress induction and physiological data collection (i.e., systolic [SBP] and diastolic [DBP] blood pressure) procedures.

Aim 2A: Evaluate feasibility of stress induction via significant change in BP from baseline to stressor.

Aim 2B: Examine acceptability of physiological data collection concurrent with stressor task via focus group.

Aim 3: Evaluate sensitivity and responsiveness to change of outcome measures. Examining these qualities and pre-post changes in physiological and psychological resilience and PTSD symptoms will provide crucial information regarding relationships between the intervention and changes in relevant variables.

3) Background

Posttraumatic stress disorder (PTSD) is a significant public health concern¹ that negatively impacts quality of life and functioning,¹⁻³ is associated with increased mortality,⁴ and poses an economic burden.⁵

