Physiological resilience is another promising mechanism, and is defined as the capacity of a biological system to avoid shifting away from baseline (e.g., “reactivity”) or to return to baseline (e.g., “recovery”).⁴⁵ The sympathetic nervous system (SNS) has served as an indicator of physiological resilience among veterans.⁴⁶⁻⁴⁸ Specifically, physiological resilience is indicated by the magnitude of peripheral vasoconstriction,⁴⁸ directly related to blood pressure (BP).⁴⁹ BP has been conceptualized as an indicator of physiological resilience to negative health outcomes.⁵⁰ Combat veterans with PTSD exhibit low physiological resilience via exaggerated BP reactivity to acute stress.^{51,52} Other research has found that trauma is predictive of lower physiological resilience.⁵³ MBSR⁵⁴⁻⁵⁸ and resilience-based⁵⁹ interventions reduce BP, improve physiological resilience,^{60,61} including among military personnel.⁶² Prior to conducting a fully-powered mechanistic RCT, central research methods such as intervention, stress induction, and physiological data collection must be validated.

Feasibility and acceptability must be established. Although some studies have conducted RCTs of MBSR among veterans with PTSD,²³ feasibility and acceptability limitations remain. A systematic review currently under review by the PI found that MBIs for PTSD showed an average attrition rate of 21.3%; much higher than the general population.⁶³ The reason for this difference is unknown. A recent meta-analysis called for increased efforts to improve the feasibility and acceptability of MBIs.⁶³ Similarly, a recent review reported that data regarding adherence in MBSR (e.g. at-home meditation practice) is underreported in most studies.⁶⁴ No studies have evaluated the feasibility and acceptability of these facets of MBSR among veterans with PTSD. Further, no study has evaluated the feasibility and acceptability of a stressor task and concurrent physiological data collection in veterans. These aspects of feasibility require further study, as recent research has emphasized the need for stress induction tasks that are feasible and reproducible.⁶⁵ Given the novelty of these procedures in this population, and the potential impact of the PI’s line of research among veterans underserved by status quo interventions, this KL2 application essential. To support this line of research, this KL2 will inform the resubmission of the PI’s K23 proposal and forthcoming VA CDA.

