Abbreviated Posttraumatic Stress Disorder Checklist (PCL-6), depression (PHQ-9), suicidality (PHQ-9 item 9), substance use (Alcohol Use Disorders Identification Test; Cannabis Abuse Screening Tool; Fagerstrom Nicotine Dependence Scale), medical history, self-reported medication history, current mindfulness practice, historical mindfulness experience.
Demographics
Age, gender, sex, ethnicity, BMI, marital status, education, income, employment status, military branch, era of service, years enlisted.

Upon arrival at the research lab in Hatfield Research Center (HRC) for the first study visit, study personnel will review the study consent form with the participant and solicit questions. Once the subject verbally confirms understanding and interest in participation, they will be asked to sign consent forms and will be provided copies prior to leaving the HRC building. All research activities, including interventions, will take place at OHSU. Data collection and analysis will take place in the [name] Lab in OHSU's Hatfield Research Building, and interventions will take place at OHSU's Kohler Pavilion.

Subjects will be encouraged to ask questions throughout the duration of participation.

Modifications to the Consent Process

In this study, Veterans will primarily be recruited when they see a flyer and contact the study team. The PI will not be accessing the VA electronic medical record to identify a potential patient. Once a potential participant reaches out to the PI and study from the contact information provided in the flyer, the PI or a delegated study team member will review the initial phone script to understand if the participant meets eligibility and shows interest in participation. If the veteran is interested, the study team will call the participant at an agreed upon time to conduct screening procedures over phone. If the participant is eligible, the participant will be invited to sign the OHSU informed consent form prior to randomizing to the study intervention (MBSR or HWE).

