We believe that requesting the participant to sign the consent form after screening will not adversely affect the patient as we will have a waiver to store this information in the secure network drive at OHSU. We have carefully selected the data elements as the minimum necessary in order to identify and recruit potentially eligible Veterans into this study without placing undue burden on the veterans. This is a minimal-risk study. Patients can avoid an unnecessary visit at OHSU to sign the consent form if they are ultimately determined to be not eligible after screening.

Non-English Speaking Subjects

English language reading and speaking are inclusion criteria for this study. Certain elements of the protocol such as the stressor task (Portland Arithmetic Stress Task) are not validated in other languages and would therefore not be able to be applied uniformly.

Assent of Children and Parent Permission

This is a study on Veterans so children will not be included.

Adults Unable to Consent/Decisionally Impaired

No decisionally-impaired adults will be recruited, and cognitive status will be determined during the phone screen.

6) Procedures

Aim 1 – Quantitative data: Recruitment and retention rates will be collected, compared between conditions, and evaluated in relation to previous research on MBSR recruitment and attrition.

Correlations between rates of home practice completion (e.g., self-guided meditation practice) and attrition rates per condition will be examined for relationships. This quantitative data will be used to guide focus group prompt development.

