Stress induction: **1. Baseline:** The Simple Reaction Task (SRT) will serve as a baseline for the stressor task. Participants press a key each time a number appears on the screen. The SRT has been used as a baseline for cognitive stressors in prior [name] lab studies; **2. Stress induction:** The Portland Arithmetic Stress Task (PAST)⁷⁰ is a cognitive stressor comprised of arithmetic problems titrated in difficulty. It has an adaptive failure algorithm, maintaining an error rate of ~40%. It has been shown to induce physiological stress across groups.⁷⁰⁻⁷²

Aim 3 – Quantitative data will be collected on paper and entered in REDCap by a study team member on an [name] lab computer and in-person clinical interview (i.e., Clinician-Administered PTSD Scale for DSM-5 [CAPS-5]). Using this data, we will examine sensitivity and responsiveness to change of outcomes. This Aim will be conducted in accordance with best practice guidelines,^{73,74} CONSORT recommendations,⁷⁵ and previous research.^{76,77} **Sensitivity** in both groups will be analyzed via relative efficiency; dividing the *F*-statistic for each physiological (systolic and diastolic BP) and self-report (psychological resilience and PTSD symptoms) by the largest *F*-statistic among outcomes (see Table below for measures).^{77,78} This process will clarify which outcomes are most sensitive to MBSR. To generate *F*-statistics for relative efficiency, we will conduct repeated measures ANOVAs for each outcome in both groups. **This statistical approach focuses on the degree to which measures are sensitive, not whether change is significant.** **Responsiveness to change** over time will be assessed in the MBSR group for physiological and self-report outcomes by: 1) calculating and comparing standardized mean response by subtracting baseline mean response from post-intervention mean response, and dividing by standard deviation of change^{74,79,80} and 2) examining zero-order correlations between a global impression of change measure (post-intervention) and change scores (baseline to post-intervention) for self-report outcomes.⁸¹⁻⁸³

Primary measures to be collected are listed below:

Method	Variable	Measurement Tool	Timepoints
Paper>REDCap	Psychological resilience	Brief Resilience Scale (BRS)	Pre, mid, post
Paper>REDCap	PTSD symptoms	PTSD Symptoms Checklist for DSM-5 (PCL-5)	Pre, mid, post
Paper>REDCap	Mindfulness	Five Facet Mindfulness Questionnaire (FFMQ-15)	Pre, mid, post

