Paper>REDCap	Perceived stress	Perceived Stress Scale (PSS-10)	Pre, mid, post
Paper>REDCap	Loneliness	UCLA Loneliness Scale	Pre, mid, post
Paper>REDCap	Distress	Distress tolerance scale	Pre, mid, post
Clinical interview	PTSD symptoms	Clinician-Administered PTSD Scale for DSM-5 (CAPS-5)	Pre, mid, post
CareTaker™	Physiological resilience	Blood pressure (BP)	Pre, mid, post

Stress induction: **1. Baseline:** The Simple Reaction Task (SRT) will serve as a baseline for the stressor task. Participants press a key each time a number appears on the screen. The SRT has been used as a baseline for cognitive stressors in prior [name] lab studies; **2. Stress induction:** The Portland Arithmetic Stress Task (PAST)⁷⁰ is a cognitive stressor comprised of arithmetic problems titrated in difficulty. It has an adaptive failure algorithm, maintaining an error rate of ~40%. It has been shown to induce physiological stress across groups.⁷⁰⁻⁷²

Interventions:

Mindfulness-Based Stress Reduction consists of weekly two-hour sessions for eight weeks, and a 7 hour retreat after Lab visit 3/week 8. The MBSR intervention will be facilitated by an experienced and

certified MBSR teacher. MBSR curriculum strongly encourages completion of home practice assignments (~30 minutes daily) to help integration of concepts into daily life. Participants will receive audio CDs and a DVD to help guide home practice.

Health and Wellness Education (HWE) Intervention is a didactic-based group intervention designed as an active comparator for randomized-controlled trials of MBSR. HWE provides instruction to participants regarding improving their emotional and physical health. In contrast to MBSR, there are no attempts to train participants' breathing, movement, or meditation habits or practices. HWE is administered in 8 weekly 2.5-hour classes with home practice to be completed between sessions (matched to MBSR for amount and effort). HWE also features one extended 7-hour retreat, similar to MBSR.⁸⁴ [name] (consultant) has conducted trials of MBSR among veterans with PTSD using a control group based on similar materials, and will provide mentorship to the PI in administering the control intervention. [name] and a trained RA will facilitate HWE.

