Participants will be given the opportunity to view their heart rate and blood pressure when it is taken in the lab during the baseline condition, unless they would prefer not to. Participants will not be shown their physiological data during the stressor condition due to the expected increases resulting from cognitive stress. Besides this, participants will not have access to any other data collected as a part of this study. If participants demonstrate pathological blood pressure during the course of the study, they will be notified and referred to their PCP and/or urgent care. If blood pressure reaches hypertensive crisis (180/110) the participant will be referred immediately to the emergency department. No data will be used for clinically decision-making, nor will it be entered into participants' medical records. Referrals will be made based on generic critical blood pressure values only.

b) Data and Specimen Banking

If data or specimens will be banked in a repository for future use as part of this protocol submission, describe here (or in a separate repository protocol document) where they will be stored, how long they will be stored, how they may be accessed, and who will have access to the specimens. Describe the procedures to release data or specimens, including: the process to request a release, approvals required for release, who can obtain data or specimens, and the data to be provided with specimens.

Data will be sent to a repository maintained separately from this study. They will be stored indefinitely in repository IRB #7436. Participants will be requested to consent to sharing data in the repository which will be optional. The repository investigator and members of the [name] Cognitive Neuroscience Laboratory are allowed to access the data and will have requisite HIPAA and other trainings. Please see repository protocol for details related to that study.

8) Data Analysis

Quantitative data:

Recruitment and retention rates will be collected, compared between conditions, and evaluated in relation to previous research on MBSR recruitment and attrition. Correlations between rates of home practice completion (e.g., self-guided meditation practice) and attrition rates per condition will be examined for relationships.

Within-participants baseline-to-stressor task t-tests will evaluate feasibility of physiological stress induction. Significant increases in BP from baseline to stressor will constitute effective stress induction.

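### Does Aim 1B fail because the plan does not say how home practice is recorded or how its completion rate is defined?

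*Combined protocol and SAP*

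**What the plan says.** Under 2) Objectives, Aim 1B: "Recruitment, differential retention, and home practice completion rates will be examined". The analysis, given in 6) Procedures (Aim 1) and repeated in 8) Data Analysis, is: "Correlations between rates of home practice completion (e.g., self-guided meditation practice) and attrition rates per condition will be examined for relationships". The Procedures text adds a use for the results: "This quantitative data will be used to guide focus group prompt development".

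On what is assigned, the plan is clear. The MBSR description and note d to the study schedule set about 30 minutes of practice a day, note d for all participants. The HWE description says its home practice matches MBSR in amount and effort. For MBSR, "Participants will receive audio CDs and a DVD to help guide home practice".

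On what is recorded, the plan is silent. The table introduced by "Primary measures to be collected are listed below" has eight rows, none on home practice. The schedule has no row for it, note c (questionnaires) does not list it, and Handling of Data does not name it. The one practice item is at screening, before randomisation: "current mindfulness practice, historical mindfulness experience".

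**The concern.** An outcome is named and an analysis planned, yet no instrument, timepoint, numerator or denominator is given. The Background makes this more pointed, since it gives as a reason for the study that "data regarding adherence in MBSR (e.g. at-home meditation practice) is underreported in most studies". Three consequences seem to follow.

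- Practice not recorded during the eight weeks can be recovered later only by recall, and probably not from people who have left. If it were asked only with the scheduled questionnaires (weeks 5 and 8 after randomisation), early leavers would have no value, and they are the people the correlation is about.
- Without a denominator, a rate could be taken over all assigned days. Leavers would then score low simply because they left.
- The only example of practice is meditation, which HWE does not train. It is unclear what counts as completed in that arm, and the claimed match with MBSR could not be checked.

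At stake are a descriptive feasibility result and the prompts for the week 9 focus group.

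**Working it through.** The plan states no figure for this point, so there is none to reproduce. The check has three parts.

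**1. What a correlation per condition can mean.** An attrition rate per condition is one number per arm. Across two arms that gives two points, and a correlation through two differing points is always +1 or -1. The only workable reading is at participant level within each arm: practice against whether the person left. An analyst would reach that reading unaided.

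**2. How much the timing of recording matters.** Inputs: 20 participants at 1:1 (4) Study Design and 5a), taken as 10 per arm; attrition from the Background, "MBIs for PTSD showed an average attrition rate of 21.3" per cent, a literature average and not a design assumption. Further assumptions, not in the plan: people leave after one of weeks 1 to 7, and those who leave also miss later lab visits. Timing weights are uniform, early (7:6:5:4:3:2:1) or late (1:2:3:4:5:6:7).

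Expected dropouts: 10 × 0.213 = 2.13 per arm. If c is the share of dropouts with any practice value, the correlation is undefined when no dropout has one: P = (1 - 0.213c)^10. For at least one of two arms: 1 - (1 - P)^2.

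| Recording | Timing | c | P, one arm | At least one arm |
|---|---|---|---|---|
| Weeks 5 and 8 only | uniform | 3/7 | 0.38 | 0.62 |
| | early | 6/28 | 0.63 | 0.86 |
| | late | 18/28 | 0.23 | 0.41 |
| Weekly session log | uniform | 6/7 | 0.13 | 0.25 |
| | early | 21/28 | 0.18 | 0.32 |
| | late | 27/28 | 0.10 | 0.19 |

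A session log first captures practice at week 2, so someone leaving after week 1 contributes nothing. That is why c is below 1 in the lower rows. Even with c = 1, P = 0.787^10 = 0.09 per arm and 0.17 for at least one arm, because an arm may have no dropouts. Asked only at week 8 or 9, no dropout has a value and the correlation is never defined.

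**3. How much the denominator matters.** Take someone who practises on 60% of days and leaves after two weeks (an assumed example). Over days assigned while enrolled the rate is 8.4/14 = 60%. Over all 56 days it is 8.4/56 = 15%. In simulated arms of 10 with practice unrelated to leaving (assumed mean rates 0.5 to 0.7), the 56-day denominator gave mean correlations of -0.30 to -0.74; days assigned while enrolled gave about zero (-0.004 to 0.010). The artefact belongs to one denominator, and the plan does not specify that denominator.

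**Precision in any case.** By Fisher's z with n = 10 and r = 0, the limits are tanh(±1.96/√7) = ±0.63.

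**The case for a change.** The strongest case for a change is that feasibility data are the product of this study, that underreported practice is one of its stated reasons, and that the remedy is cheap: one schedule row, a short log of at most 8 × 20 = 160 entries, and an amendment through the IRB. It can also fairly be said that the omission is not confined to the table of primary measures. The schedule, note c and the data description carry no such restriction, and they omit practice too.

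The omission stands. The inference that nothing will be collected, or that it will be collected badly, does not. The plan's lists are not complete inventories. The global impression of change measure is analysed in 8) Data Analysis but absent from the table. Heart rate and respiration rate are described under the VitalStream device but have no row there. Session attendance is paid for, at $5 a session, with no schedule row for recording it. Absence from these lists is therefore weak evidence about what staff will record.

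The point about HWE also stands as missing detail. Meditation is given only as an example, however, and that arm has its own assigned practice to count against.

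The loss of dropouts in part 2 needs practice to be asked only at lab visits, and needs leavers to skip those visits. The plan says neither.

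**Conclusion.** This is a gap that the study team can fill sensibly within the existing design, not an error in a stated rule. Weekly contact in both arms gives the occasion to record practice, and the daily assignment gives the basis for a rate. An analyst who sees that leavers have fewer assigned days will divide by days assigned while enrolled. The focus group prompts are served by a simple summary by arm.

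The figures in the working depend on assumed dropout timing, a borrowed attrition rate and, for the denominator, invented practice distributions. They show that poor choices would hurt, not that the plan makes them. Under sensible recording the correlation is undefined in about 10% to 18% of arms, and where it exists it carries about ±0.63 of uncertainty, so spelling out the measure would add little to what it can show. No threshold or efficacy conclusion rests on it, and recruitment and retention results are unaffected. No change to the plan is called for.

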The long-term goal of this research is to use mechanisms identified via a fully-powered mechanistic RCT funded by NIH K23 or VA CDA to optimize a resilience-based, trauma-informed MBI. In order to secure funding and conduct this mechanistic RCT, feasibility and acceptability of the stressor paradigm and concurrent physiological data collection, as well as the MBSR and randomization procedures must be established.

4) Study Design

The design of this study is a randomized controlled interventional study. All participants will complete three in-person lab visits, consisting of computerized questionnaires, physiological data recording, and completion of a stressor paradigm. Following completion of computerized questionnaires at the baseline visit, participants will be randomized at a 1:1 ratio using covariate adaptive randomization.

Participants will be randomized to receive Mindfulness-Based Stress Reduction (MBSR; active intervention condition) or Health and Wellness Education (HWE; control condition). Both interventions include 8 weekly in-person group sessions with an additional extended session after week 8.

5) Study Population

a) Number of Subjects

This is a single center study. We will screen approximately 40 patients of which we expect to enroll 20 participants, all of whom will be veterans experiencing PTSD symptoms (PTSD symptoms will be confirmed during telephone screen). Therefore, 20 participants will sign the consent form and be included in this study.

b) Inclusion and Exclusion Criteria

Participants will be screened over phone to determine eligibility. Subjects will be aged 18-85 years. Subjects older than 85 years of age will be excluded due to their decreased ability to tolerate the experimental procedures because of potential cognitive decline and inability to sustain the attention needed for the Portland Arithmetic Stress Task (PAST), as well as the decreased ability to remain still during the intervention conditions due to musculoskeletal aches and pains and decreased flexibility frequently seen in aging.

Inclusion criteria	Exclusion criteria
Adult (18-85 years)	Pregnancy
Military veteran	Severe untreated depression, cognitive impairment, or active suicidality*
Experiencing PTSD symptoms	Life-threatening or severely disabling medical conditions
Reading and speaking in English	Excessive use of alcohol, nicotine, or cannabis†

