Sensitivity in both groups will be analyzed via relative efficiency; dividing the F-statistic for each physiological (systolic and diastolic BP) and self-report (psychological resilience and PTSD symptoms) by the largest F-statistic among outcomes (see Table above for measures).^{77,78} This process will clarify which outcomes are most sensitive to MBSR. To generate F-statistics for relative efficiency, we will conduct repeated measures ANOVAs for each outcome in both groups. This statistical approach focuses on the degree to which measures are sensitive, not whether change is significant. Responsiveness to change over time will be assessed in the MBSR group for physiological and self-report outcomes by: 1) calculating and comparing standardized mean response by subtracting baseline mean response from post-intervention mean response, and dividing by standard deviation of change^{74,79,80} and 2) examining zero-order correlations between

a global impression of change measure (post-intervention) and change scores (baseline to post-intervention) for self-report outcomes.⁸¹⁻⁸³

Qualitative data:

A thematic analysis approach⁶⁷ to qualitative data will explore participant experiences to understand feasibility, acceptability, and impact of assessments, protocol, and interventions.

Analysis process will consist of: 1) familiarization, 2) initial coding, 3) creating themes, 4) reviewing themes, 5) defining and naming themes, and 6) data interpretation.

9) Privacy, Confidentiality and Data Security

Standard institutional practices will be followed as described in the OHSU Information Security Directives (<http://www.ohsu.edu/xd/about/services/integrity/policies/ips-policies-info-sec-directiv.cfm#results>) to maintain the confidentiality and security of data collected in this study. Study staff will be trained with regard to these procedures. Any staff that will be involved in these research activities will have completed the requisite Human Subject Protection Training as required by the IRB prior to engagement.

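### Aim 3 ranks outcomes by F ratios and standardised response means without any uncertainty, in about 10 MBSR participants, and cannot clarify which outcome is most sensitive

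*Combined protocol and SAP*

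**What the plan says.** The Aim 3 analysis appears in section 6 (Procedures, Aim 3) and again in section 8 (Data Analysis, Quantitative data). It uses two indices.

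- **Sensitivity.** Relative efficiency is obtained by "dividing the F-statistic for each physiological (systolic and diastolic BP) and self-report (psychological resilience and PTSD symptoms") "by the largest F-statistic among outcomes". The F-statistics come from repeated measures ANOVAs in both groups. The plan does not say whether F is for time within an arm, time pooled over arms, or group by time. The stated result is: "This process will clarify which outcomes are most sensitive to MBSR".
- **Responsiveness.** In the MBSR group only, the plan proposes "calculating and comparing standardized mean response by subtracting baseline mean response from post-intervention mean response", divided by the standard deviation of change. This is the SRM. For self-report outcomes it adds correlations with a global impression of change.

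Neither index is given a standard error, an interval or a ranking probability. The plan does say that the focus is on degree of sensitivity and not on significance.

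On size, section 5a says "Therefore, 20 participants will sign the consent form and be included in this study", and section 4 says "participants will be randomized at a 1:1 ratio using covariate adaptive randomization". No precision or power rationale is given for 20.

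**The concern.** Both indices are estimates from about 10 people. Read as point values, they will show a clear order among outcomes whether or not one exists. The top outcome has a relative efficiency of exactly 1 by construction and every other outcome falls below it, so a table of ratios such as 1, 0.6, 0.4 and 0.2 looks informative even when the true ratios are all 1.

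The Objectives say that the study is to support a grant resubmission, and Background describes a later, fully powered mechanistic trial. A ranking presented as settled could carry more weight in planning that trial than the data can bear. No efficacy conclusion depends on it.

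**Working it through.** **There is no planning figure to reproduce.** The enrolment of 20 comes with no alpha, power, effect size or precision target.

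**Inputs from the documents**
- 20 participants, 1:1: 20 / 2 = 10 in the MBSR arm.
- Attrition of 21.3% (Background, an average from a review and not a planning input): 10 × (1 − 0.213) = 7.87, about 8 completers.
- Three visits (pre, mid, post).
- Four outcomes: systolic BP, diastolic BP, psychological resilience and PTSD symptoms. There would be five if PCL-5 and CAPS-5 were ranked separately.

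**Inputs assumed, because the documents give none**
- Normal data, linear change over visits, equal error variance at each visit.
- Correlation between outcomes 0.3 (range 0 to 0.6).
- True SRMs as listed below.
- F for time within the MBSR arm.

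**Formulas**
- SRM = mean(post − pre) / SD(post − pre).
- F = [SS(time) / 2] / [SS(residual) / (2(n − 1))].
- Relative efficiency = F / largest F among the outcomes.

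**Step 1: all four outcomes equally responsive (SRM 0.5).** The true ratios are all 1. Simulation (40,000 runs per row) gives:

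| n | Median ratios, lowest to highest | Lowest ratio below 0.5 |
|---|---|---|
| 8 | 0.14, 0.34, 0.62, 1 | 95% |
| 10 | 0.16, 0.36, 0.63, 1 | 94% |
| 20 | 0.24, 0.45, 0.70, 1 | 89% |

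With correlations from 0 to 0.6 at n = 10, the median lowest ratio runs from 0.12 to 0.23. The n = 20 row needs a time F pooled over arms and a pooled change of the same size, which the plan does not state.

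**Step 2: comparing SRMs.** Two outcomes with equal true SRM 0.5 show observed SRMs that differ by about −0.95 to +0.94 (95% range) at n = 10. The half-width is 0.72 to 1.03 for correlations from 0.6 down to 0. From the noncentral t distribution, a single observed SRM of 0.5 has a 95% interval of −0.17 to 1.15 at n = 10 and −0.25 to 1.22 at n = 8.

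**Step 3: one outcome truly best, three equal below it (n = 10, correlation 0.3).**

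| True SRMs, best v others | Wrong outcome has the largest F |
|---|---|
| 0.6 v 0.5 | 67% |
| 0.8 v 0.5 | 48% |
| 1.0 v 0.5 | 29% |
| 1.2 v 0.4 | 11% |

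If F is instead group by time with 10 per arm and no change in the control arm, the 0.8 v 0.5 figure becomes 57%.

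**Step 4: is the denominator the cause?** Dividing every F by the same number cannot change their order, so using the largest F causes none of the wrong picks. A fixed reference outcome does not remove the noise either: with equal outcomes at n = 10, the ratio of one F to another has a 95% range of about 0.05 to 22. Sample size does matter. For 0.8 v 0.5 at correlation 0.3, wrong picks fall from 48% at n = 10 to 33% at n = 20 and about 9% at n = 60.

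**The case against.** The strongest reply is that this is a 20-person feasibility study and the plan expressly sets significance aside in favour of degree. It does not rule out intervals, and it adds a second check through the global impression of change. Part of this stands. Silence on intervals is not a refusal, and no efficacy claim is at risk. But declining to test does not remove sampling error from an estimated degree. The second check covers self-report outcomes only and has no stated precision, so it cannot settle blood pressure against questionnaires.

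Three stronger readings are tempting, and the documents do not support them.

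- A reader might infer that the plan will name the wrong best outcome about half the time. That fits one assumed gap (0.8 v 0.5) at about 8 to 10 participants. The documents give no effect sizes, and the rate moves widely with the gap. If all outcomes are equal, no pick is wrong.
- A reader might infer that dividing by the observed maximum is the fault. It forces a ceiling of 1, but Step 4 shows that it alters neither the order nor the noise.
- A reader might infer that Aim 3 will select one outcome and discard the rest. The plan contains no threshold, drop rule or commitment to a single outcome.

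**Conclusion.** The concern holds in this form: both indices are planned without uncertainty, and at about 10 MBSR participants (about 8 after the cited attrition) they cannot do what the plan says they will. Under the stated assumptions, equally responsive outcomes appear to differ at least twofold in relative efficiency in about 94% of trials, and two equal SRMs can differ by nearly 1 in either direction. The chance of ranking the wrong outcome first at n = 10 runs from about 11% to 67% across the gaps examined, so it should be quoted only with the gap assumed. The cause is sampling error at this size.

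The size of the effect rests on assumed SRMs, correlations and choice of F. The absence of any uncertainty measure does not. The point should be corrected before analysis; it affects the reading of Aim 3 and not the feasibility aims.

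**What to change.** In section 8, and in the matching text of section 6:

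1. State which F is used: time within the MBSR arm, time pooled over arms, or group by time.
2. Report a 95% interval for each relative efficiency, each SRM and each pairwise SRM difference, from a bootstrap that resamples participants so that outcomes stay paired.
3. Report how often each outcome ranks first across the resamples.
4. Replace the promise that the process clarifies which outcomes are most sensitive with a statement that it estimates their relative sensitivity, and call the ranking descriptive.

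No fixed reference outcome and no rule based on intervals excluding equality is needed.

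The cost is some analysis-plan wording and a short script, with no new data. There are two downsides. Bootstrap intervals are only approximate at n = 10 (percentile coverage for an SRM difference was about 91% in simulation), and few or no outcomes are likely to be clearly separated.
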